With the participant seated comfortably, a small air-filled disposable bulb will be placed in the mouth, behind the front teeth, and the participant will be instructed to press as hard as they can with the front and back of the tongue, three times in each position, with 30 seconds of rest between each trial. Next, participants will be asked to swallow their saliva with the bulb at the front of their tongue, three times, with 60 seconds between each swallow. Measures will be recorded on the Tongue Strength Measurement form.

Videofluoroscopy (30 minutes):

A videofluoroscopy (i.e., swallowing x-ray) will be conducted by a speech-language pathologist and a radiology technician, at the Swallow Systems Core laboratory in Gainesville, Florida. [name] and the co-director of the Swallowing Systems Core lab own a C-Arm fluoroscopy unit that is housed in their secure research space. This C-Arm will be used to conduct all swallowing studies. This procedure will take approximately 30 minutes of the participant's time (including set-up, instructions) and will include up to 21 liquid bolus trials.

An array of barium stimuli has been developed for this study. These stimuli include thin, slightly-thick, mildly-thick, moderately- and extremely-thick liquids, defined by the International Dysphagia Diet Standardisation Initiative (IDDSI) framework. The barium stimuli used for videofluoroscopy will be prepared using E-Z-Paque® barium in 20% w/v barium concentration with starch and gum-based thickening agents (Nestlé Resource® ThickenUp® and ThickenUp Clear®). All stimuli will be prepared at the Swallowing Systems Core Laboratory, within 3 hours of the scheduled videofluoroscopy, according to a strict standard operating procedure. Following preparation, stimuli will be stored in the lab until needed.

Boluses will be presented in the following order:

- a) Three (3) swallows of Level 0 thin liquid (Bracco E-Z-Paque powdered barium, prepared in a 20% weight-to-volume concentration);
- b) Six (6) swallows of Level 1 slightly thick liquid (20% weight-to-volume barium concentration):
 - Three (3) boluses thickened with a xanthan-gum thickener (Nestlé Thicken Up Clear),
 - Three (3) boluses thickened with a starch thickener (Nestlé Thicken Up);
- c) Three (3) swallows of Level 2 thick liquid (20% weight-to-volume barium concentration, thickened with a xanthan-gum thickener (Nestlé Thicken Up Clear);

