Throughout the study, steps will be taken to ensure participant safety and minimize risk of adverse events. We anticipate that comprehensive examinations of the full continuum of liquid consistencies may not be possible for all patients in this study, and we will adhere to strict rules to terminate the protocol, if necessary. If aspiration or penetration leaving residue in the laryngeal vestibule is observed on two trials of the same stimulus, the remaining trial(s) of that stimulus will be skipped and the examiner will move on to the next IDDSI level. If a participant displays 3 instances of aspiration (PAS ≥ 6), the swallowing x-ray will be stopped and data collection will discontinue for that participant. The protocol will be terminated after 3 observations of penetration-aspiration. If severe levels of pharyngeal residue are observed in an individual (i.e., either the valleculae or pyriform sinuses are judged to be 75% full or more, with risk of overflowing) and persist despite compensatory maneuvers, the swallowing x-ray will be terminated and the participant's dysphagia will be managed according to best practice standards of care.

After the initial swallow of each bolus is collected for research purposes, the attending speech-language pathologist may instruct the patient to perform additional tasks (such as coughing) or clearing swallows using compensatory maneuvers (e.g. chin down position) to manage instances of aspiration or residue, as deemed clinically necessary. These subsequent swallows using compensatory maneuvers will be noted on the appropriate Videofluoroscopy Clinical Reporting Form and will not be included in the data analysis. The attending clinician may terminate the protocol at any time if he or she deems the patient to be at significant risk for adverse events.

In the event of an unanticipated adverse response, the participant's neurologist will be immediately notified and the patient will be seen for a complete evaluation. Data, adverse events, and individual subject safety are monitored throughout each subject's evaluation as well as during weekly laboratory meetings with the PI and study team.

Data Processing and Analysis

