All data processing will take place at the University Health Network, Toronto Rehabilitation Institute. Full-length videofluoroscopies will be transferred from the University of Florida to the Swallowing Rehabilitation Research Lab at the Toronto Rehabilitation Institute through a secure file transfer protocol.

An engineer from [name] research team will segment each videofluoroscopy into individual bolus clips (i.e., one video clip, per bolus). Bolus-level videos will be de-identified to the highest possible degree and randomized for blinded analysis. Videofluoroscopy rating will follow a standard operating procedure, developed in the Swallowing Rehabilitation Research Lab. A minimum of twenty-five percent (25%) of the videos will be rated in duplicate to obtain measures of inter- and intra-rater agreement.

Planned Statistical Analysis

Once the videofluoroscopy ratings have been completed, statistical analysis will be completed either in [name] laboratory or in [name] laboratory. Transfer of anonymized excel data sheets containing the information needed for these analyses will be covered by a data transfer and sharing agreement.

Statistical analysis will be conducted in a stepwise fashion, to address the research questions and identify trends within the data. We will begin by exploring correlations between measures of interest, to identify and appropriately address potential non-independence and collinearity. If two or more measures are found to be highly correlated with one another, we will retain the measure(s) which show the least variability and remove the remaining measures from the analysis. Further, because we are obtaining multiple bolus trials from the same participants, we will also calculate within-subject variance for each parameter of swallowing physiology and function.

We will explore how parameters of swallowing physiology vary based on swallowing function status (i.e., swallowing safety or efficiency) through a series of repeated measures ANOVAs, Spearman's Rho and Pearson's correlation coefficients, and logistic regression (statistical tests will be defined by the type of data). Following this, we will explore how liquid thickness modulates the relationships between parameters of swallowing physiology and function, as a covariate, using a path analysis.

Privacy and Confidentiality

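### Whether thicker boluses are observed depends on safety events at thinner levels, and the plan does not say how truncated exams enter comparisons by thickness

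*Combined protocol and SAP*

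**What the plan says.** All references are to the combined protocol and SAP.

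- **Order (section 6, Videofluoroscopy).** "Boluses will be presented in the following order": three Level 0 boluses, six Level 1, three Level 2, six Level 3 and three Level 4, up to 21 in all. Only thickener type is randomized.
- **Skips and stops (section 6, Safety Precautions).** "If aspiration or penetration leaving residue in the laryngeal vestibule is observed on two trials of the same stimulus", then "the remaining trial(s) of that stimulus will be skipped and the examiner will move on to the next IDDSI level". The exam ends on three aspirations: "If a participant displays 3 instances of aspiration (PAS ≥ 6), the swallowing x-ray will be stopped and data collection will discontinue". The next sentence counts a different event: "The protocol will be terminated after 3 observations of penetration-aspiration". Persistent severe residue also ends the exam, and "The attending clinician may terminate the protocol at any time" if the risk is judged significant.
- **Expectation of incomplete exams (same section).** "We anticipate that comprehensive examinations of the full continuum of liquid consistencies may not be possible for all patients in this study".
- **Use of the comparison (section 5, Aim 2).** One of two primary research questions. Thickness is to be explored for its influence on safety and efficiency, with a view to the efficacy of thickened liquids and the best thickness for treatment.
- **Analysis (section 6, Planned Statistical Analysis).** Physiology is compared by function status "through a series of repeated measures ANOVAs", correlations and logistic regression, with the test chosen by data type. Thickness enters as a covariate in a path analysis. Within-subject variance will be calculated because each participant gives several boluses. Nothing is said about skipped boluses, stopped exams or a participant effect in a comparison by thickness.

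**The concern.** Participants who aspirate early contribute thin-liquid boluses and then leave. Those who reach Level 4 are selected for having had few events. If risk is a fairly stable trait of the participant, the thick-liquid boluses come from a lower-risk group than the thin-liquid boluses, and the raw aspiration rate falls with thickness even when thickness does nothing. Stable differences in risk are plausible here: one sample of 40 mixes ALS and Parkinson's disease, with bulbar, spinal or mixed onset in ALS.

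The simplest uses of the listed tools do not remove this. Logistic regression on the delivered boluses inherits the selection. Classical repeated measures ANOVA drops incomplete exams and selects in another way. Since Aim 2 is meant to inform the efficacy of thickening, an unstated choice between these could decide its conclusion.

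**Working it through.** **Inputs from the documents.** Seven stimuli of three trials in the fixed order; the two-event skip; a stop on three events; N=40. The documents give no aspiration rate, between-participant spread or expected share of incomplete exams, so there is no figure of the plan's own to reproduce on this point. The sample-size calculation concerns bolus-flow timing and does not bear on it.

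**Assumptions.** Mean per-bolus aspiration 5, 10 or 20%; participant logit SD 0 to 3; a thickness effect common to all participants. Penetration with residue and any penetration lie 0.5 and 1 logit below aspiration. Stop A counts three aspirations. Stop B counts three penetrations or aspirations; the text gives no PAS cut-off for this, so reading it as any penetration is an assumption. Residue and clinician-discretion stops are not simulated.

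**Step 1: one worked case.** Take a simpler version in which a single event type drives both skip and stop, with a 10% rate, SD 2 and no thickness effect. 78% of participants reach Level 4.
- Pooled rates: 9.48% at Level 0 and 3.49% at Level 4. Risk ratio 0.0349/0.0948 = 0.37. Odds ratio (0.0349/0.9651)/(0.0948/0.9052) = 0.0362/0.1047 = 0.35. The truth is 1.
- Only those who reach Level 4: 2.58% at Level 0 and 3.49% at Level 4. Risk ratio 0.0349/0.0258 = 1.35, an error the other way.
- Random-intercept logistic model on all delivered boluses: odds ratio 1.01.

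**Step 2: full design, pooled odds ratio, SD 1-3** (200,000 participants per cell).

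| Truth | Contrast | Stop A | Stop B |
|---|---|---|---|
| No effect | Level 1 vs 0 | 0.57-0.96 | lower |
| No effect | Level 4 vs 0 | 0.17-0.79 | 0.08-0.55 |
| Protective, marginal OR 0.42-0.63 | Level 4 vs 0 | 0.09-0.36 | 0.04-0.26 |
| Harmful, marginal OR 1.54-2.30 | Level 4 vs 0 | 0.30-1.67 | 0.13-1.08 |

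With SD 0 and no effect, the Level 4 vs 0 value is 0.99-1.02. With true harm, the pooled value falls below 1 in 7 of 9 cells (A) and 8 of 9 (B). With no effect, 47-90% (A) or 17-83% (B) of participants reach Level 4.

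**Step 3: completers, risk difference Level 4 minus 0, in percentage points.**
- No effect: +0.1 to +1.1 (all 21 boluses) or +0.2 to +4.2 (at least one bolus per level).
- Protective, truth -2.1 to -9.8: -0.4 to -3.2 and -0.3 to -2.3 respectively, so protection is understated.
- Harmful under A, truth +3.2 to +14.6: +1.1 to +6.6 for all-21 completers, so harm is understated, the same direction of error as pooling.

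**Step 4: N=40, no effect.** Pooled logistic regression falsely shows protection in 5-96% (A) and 14-99% (B) of studies. Cluster-robust errors give 6-93% and 15-98%: they repair the standard error, not the estimate. A four-category ordinal mixed model with a linear trend has 4-7% false positives in total and a median odds ratio of 0.93-1.05.

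**Step 5: why ordinal.** If stops also count penetration, a mixed model of aspiration alone omits part of what drives them. Under stop B with no effect it gives 0.50-0.69 in large samples; the ordinal model, checked in the same cells under both stops, gives 0.98-1.03.

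**Step 6: limits of the mixed model.**
- Power for a true conditional odds ratio of 0.8^4 = 0.41 is 50-73% (A) and 29-49% (B).
- If thickness lowers only penetration, the common-effect model gives 0.41-0.44 although aspiration is unchanged. A separate aspiration effect returns 0.97-1.19 for aspiration (not run at N=40).
- If risk falls into two classes, the normal-intercept model gives 0.35-1.07 with no effect (pooled: 0.01-0.75).
- If thickness effects vary by participant (20% rate, SD 2, slope SD 0.5 per level), the linear-trend model on full versus truncated data gave 1.44 vs 1.15 (A, intercept-slope correlation 0) and 0.99 vs 1.55 (B, correlation -0.5).

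**The case against.** The strongest reply is that the plan never says it will pool. ANOVA and logistic regression are tied to physiology by function status, not to safety by thickness, and the section shows awareness of clustering. That stands: a reader might infer that a biased analysis is planned, and the text does not support this. But calculating within-subject variance does not address truncation, and no other method is named for the comparison that Aim 2 needs.

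A reader might also infer that differing risk alone guarantees overstated protection. It does not; risk must carry over from thin to thick liquid. With thickness effects perfectly negatively correlated with baseline risk, under stop A, the bias vanished (pooled 1.00, true 1.00 at 5%, SD 1, slope SD 0.5 per level) or reversed (pooled 0.86, true 0.60 at 20%, SD 2, slope SD 0.75). That is an extreme case; at a correlation of -0.5 the usual direction remained in every cell run.

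Third, Level 4 vs 0 is the most extreme contrast and every rate is assumed. At 5% and SD 1 under stop A, pooled odds ratios for Levels 1, 2 and 3 are only 0.96, 0.92 and 0.84. The ranges show what is possible, not what will happen.

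Finally, the aims are worded as exploratory. That limits the claims the study can make, but an error that can reverse the sign matters for exploratory estimates too.

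**Conclusion.** The concern holds as a gap in the analysis plan. Observation of thicker boluses depends on earlier safety outcomes by design, and no handling is stated. Pooling the delivered boluses overstates protection if participants differ in risk and that risk tends to persist across thickness; cluster-robust errors do not correct it. Restricting to completers errs the other way on the risk-difference scale when thickness has no effect or protects. On the odds-ratio scale its direction depends on who counts as a completer and on the estimator.

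The size cannot be stated from the documents. The ranges rest on the assumed rates, SDs, thresholds and common thickness effect. The bias is larger if the stop counts any penetration-aspiration. The direction of any bias in residue and timing measures was not derived. It would also go too far to read the mixed model as a complete cure: it relies on its random-effects assumptions and has limited power at N=40.

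**What to change.** In Planned Statistical Analysis, state how truncated exams are analysed:

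- For safety by thickness, do not rely on raw per-level rates, pooled logistic regression or complete-case ANOVA. Make the main analysis a likelihood-based mixed model on every delivered bolus, with a participant random intercept and thickness as a within-participant factor or, if Level 4 is sparse, a trend.
- Keep the safety outcome ordinal and fine enough to capture the events that trigger skips and stops (safe, penetration without residue, penetration with residue, aspiration). Simplify it if unstable at N=40.
- Include participant effects in the path analysis.
- Report participants and boluses reaching each level, and the reason for each skip or stop.
- As sensitivity checks where data allow, give aspiration its own thickness effect, let the thickness slope vary by participant, and relax the intercept distribution.
- State as limitations that thickness is confounded with presentation order, that residue and clinician-discretion stops may depend on unmodelled information, that the model depends on its random-effects assumptions, and that power is limited.

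The two stop sentences in Safety Precautions count different events and must be reconciled, because the amount of truncation depends on which applies. No change to the safety rules is proposed.

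The cost is a few sentences and extra modelling work. No new data, participants or procedures are needed.

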Videofluoroscopy (i.e., dynamic swallow x-ray) is widely considered to be the “gold standard” method for determining the nature, severity and functional consequences of abnormal swallowing physiology. Although observations from videofluoroscopy are frequently described in research literature, few studies have used objective measures to quantify the impairments and pathophysiological changes in swallowing. This makes it difficult to compare results directly across research studies, determine at what point physiological changes contribute to functional impairments in swallowing, and explore what factors lead to changes in swallowing physiology. Changes in liquid thickness, for example, have been shown to influence swallowing physiology in a predictable manner in healthy individuals and patients post-stroke; however we do not know how changes in liquid thickness modulate swallowing physiology in individuals with neurodegenerative diseases.

The purpose of this study is to conduct quantitative analysis of swallowing physiology, seen on videofluoroscopy (swallow x-ray), in order to:

- 1) Identify physiological parameters contributing to swallowing impairment; and
- 2) Determine how swallowing physiology and function differs across five levels of liquid thickness: thin, slightly-thick, mildly-thick, moderately-thick and extremely-thick.

4. Background

Dysphagia (i.e., swallowing impairment) is often characterized in terms of:

- (1) Impaired safety (i.e., food and liquids entering the airway, known as aspiration), and;
- (2) Impaired efficiency (e.g., food and liquids leaving residue in the throat after the swallow).

Impaired swallowing safety is linked to pneumonia while impaired efficiency has been indicated as a risk factor for malnutrition. Further, the accumulation of residue in the throat poses an independent risk factor for subsequent aspiration events. Dysphagia is highly prevalent in individuals with neurodegenerative diseases, such as Amyotrophic Lateral Sclerosis (ALS) and Parkinson's Disease (PD). As there is currently no cure for these complex diseases, symptomatic management of dysphagia is the current standard of care.

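### Residue already present when a bolus begins is not accounted for, so with a fixed ascending order carry-over can bias the thin-versus-thickened comparison

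*Combined protocol and SAP*

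**What the plan says.** All places are in the combined protocol and SAP.

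- **Order.** Under Videofluoroscopy (section 6), the list headed "Boluses will be presented in the following order" runs Level 0 (3 swallows), Level 1 (6), Level 2 (3), Level 3 (6), Level 4 (3). The session "will include up to 21 liquid bolus trials". Only thickener type is randomised.
- **What is analysed.** Safety Precautions makes the first swallow the research swallow: "After the initial swallow of each bolus is collected for research purposes", the clinician may ask for coughing or clearing swallows "to manage instances of aspiration or residue, as deemed clinically necessary". Those later swallows that use compensatory manoeuvres "will be noted on the appropriate Videofluoroscopy Clinical Reporting Form and will not be included in the data analysis".
- **Limit on residue.** The only one stated is in the same section: the examination ends if the valleculae or pyriform sinuses are at least 75% full and manoeuvres do not resolve this.
- **Outcomes.** Section 5 takes post-swallow residue as the efficiency outcome and penetration-aspiration as the safety outcome.
- **Mechanism.** Section 4 (Background) states that "the accumulation of residue in the throat poses an independent risk factor for subsequent aspiration events".
- **Rating and analysis.** Data Processing and Analysis cuts each recording into one clip per bolus, in random order, rated blind under a standard operating procedure that is not reproduced. Planned Statistical Analysis names correlations, repeated measures ANOVA, logistic regression and a path analysis with thickness as covariate. It plans to calculate within-subject variance "because we are obtaining multiple bolus trials from the same participants". It names no term for starting residue, preceding clearing or the previous bolus.

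**The concern.** What is in the throat when a bolus arrives can affect that bolus's residue score and its chance of aspiration. The protocol says as much about aspiration. In every participant, thicker boluses come later, so thickness and swallowing history rise together. The first thin bolus is the only one with no study bolus before it. If starting residue is ignored, part of any difference between thin and thickened liquids may be carry-over.

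Aim 2 is meant to inform the choice of a therapeutic thickness, and the thin-versus-thickened contrast is central to it. Aim 1 is touched as well: clearing is prompted by aspiration or residue, so the amount carried over will differ between more and less impaired participants. Calculating within-subject variance does not deal with this, because the dependence runs from one bolus to the next.

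**Working it through.** The plan gives no figure for carry-over. Its one calculated figure, 36 participants, does not enter this point. (A two-sided paired t-test with d = 0.5, alpha 0.05 and 80% power gives 34, which is close.)

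**Transitions.** The listed order has 3 + 6 + 3 + 6 + 3 = 21 boluses, hence 20 bolus-to-bolus transitions. Of these, 4 go to a thicker level, 2 change thickener within a level, and 14 repeat the same stimulus. Carry-over therefore mostly falls on a bolus of the same thickness. It becomes confounded with thickness through accumulation over the sequence.

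**Illustrative model.** Assumptions: each bolus leaves the same new residue r at every level (no thickness effect); a share c of existing residue remains after the next swallow; the throat starts clear; there is no clearing and no early stopping. Then

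R_k = c·R_(k−1) + r, so R_k = r(1 − c^k)/(1 − c).

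The Level 0 mean over k = 1, 2, 3 is r(3 + 2c + c²)/3:

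- c = 0.2: 3.44/3 = 1.147r
- c = 0.4: 3.96/3 = 1.320r
- c = 0.6: 4.56/3 = 1.520r

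By Level 4 the value is practically the limit r/(1 − c). The range of c is assumed.

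| c | Level 0 | Level 1 | Level 4 | Level 4 / Level 0 | Level 4 / Level 1 | Share of rise complete by Level 1 |
|---|---|---|---|---|---|---|
| 0 | 1.000r | 1.000r | 1.000r | 1.00 | 1.00 | – |
| 0.2 | 1.147r | 1.250r | 1.250r | 1.09 | 1.0003 | 99.6% |
| 0.4 | 1.320r | 1.655r | 1.667r | 1.26 | 1.007 | 96.6% |
| 0.6 | 1.520r | 2.371r | 2.500r | 1.64 | 1.054 | 86.9% |

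The false effect is a step between thin and everything else, followed by a plateau.

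**Does measured starting residue remove it?** Let S_k be the residue present just before bolus k. In this model R_k = r + c·S_k, whether or not clearing came before. At c = 0.4, mean S at Level 0 is (0 + 1 + 1.4)/3 = 0.8r and at Level 4 about 1.667r. Subtracting c·S gives 1.320r − 0.320r = r and 1.667r − 0.667r = r, so the false difference disappears. At c = 0 there is nothing to remove.

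**Would the previous bolus's post-swallow rating do instead?** No, because it is taken before any clearing. At c = 0.4 on the plateau, suppose clearing removes all residue before bolus k. The previous rating is 1.667r and implies R_k = r + 0.4 × 1.667r = 1.667r, but the true value is r, an error of 0.667r. That rating also carries participant severity. In a pooled model with no carry-over (assumed true slope 0.3 per level, residual SD 1), adjusting for it shrank the slope to 0.25 with a between-participant SD of 0.5, and to 0.16 with an SD of 1. Hence the need for participant effects.

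**The case against.** The strongest reply is that the documents show something unstated rather than an error. The rating procedure is not reproduced and may already say how pre-existing residue, or aspiration of it, is scored. No model formula is given either. This stands: carry-over can be scored against a later bolus, but the documents do not show that it will be. If the procedure covers starting residue, a sentence in the plan and a term in the models settle the point.

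The illustration also leaves out clearing and early stopping, both of which the protocol provides for. Clearing would reduce carry-over, and stopping removes the worst cases from the thicker levels, so the net bias is not known. This stands too.

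Three stronger readings are tempting, and the documents do not support them:

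- *Residue is left out of the analysis.* It is the efficiency outcome. Only later swallows using compensatory manoeuvres are excluded.
- *That exclusion creates the bias.* Analysing the initial swallow is a coherent rule, and clearing tends to lessen carry-over. The source is the ascending order with no account of starting residue.
- *Carry-over mimics a steady rise with thickness, each bolus loading the next, thicker one.* Only 4 of 20 transitions step up a level, and under the model there is little change from Level 1 upward.

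None of this supplies the missing starting value in the planned analysis.

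**Conclusion.** The point holds in limited form. With a fixed ascending order, discretionary clearing and no starting-residue or clearing term in the analysis, residue left by earlier boluses can be confounded with thickness. The protocol itself names the mechanism for aspiration. The contrast at risk is mainly thin against thickened liquid in Aim 2; comparisons among the thickened levels are much less affected at the values of c examined.

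The documents do not fix the size. The excess of 9% to 64% at Level 4 over Level 0 rests on assumed c from 0.2 to 0.6, equal new residue per bolus, no clearing and no early stopping. It shows what is possible and is not an estimate. The gap is worth closing before the ratings are analysed, because the remedy is cheap and uses recordings that will already exist.

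**What to change.** 1. **Rate starting residue.** The same blinded raters score residue on the last frame before each bolus enters, on the scale used after the swallow. The plan does not say where a clip begins, but full-length recordings are transferred, so the frame can be taken from them where the clip starts too late. If the rating procedure already does this, say so in the plan.
2. **Use it.** Include starting residue and a preceding-clearing indicator, taken from the Videofluoroscopy Clinical Reporting Form, in the residue and safety models, together with participant effects. State whether spontaneous clearing swallows are recorded on that form; the text clearly covers only those using compensatory manoeuvres.
3. **Do not substitute** the previous bolus's post-swallow rating.
4. **Treat as exploratory** any analysis limited to boluses that start with no residue, since it selects less impaired participants.

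Order terms alone will not do, because order and thickness are nearly collinear here. For the same reason, the adjustment deals with carried-over residue only; other effects of order, such as fatigue, stay confounded with thickness.

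Cost: one extra rating per existing clip and transcription of one form item. Clinical care, bolus order and sample size are unchanged.
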